Subjects must be discontinued from study drug for an ECG change considered clinically significant and with reasonable possibility of relationship to study drug OR a confirmed absolute Fridericia's correction formula (QTcF) value > 500 msec or confirmed increase of ≥ 60 msec from Baseline.

Management of Muscle-Related Symptoms

If a subject experiences symptoms suggestive of myositis or rhabdomyolysis, CPK and aldolase measurements should be requested and will be provided after review by the TA MD with clinical management and/or study drug interruption as deemed appropriate by the treating physician. Please refer to [Table 4](#) below for further instructions.

Management of Thrombosis Events

Subjects who develop symptoms of thrombosis should be promptly evaluated and treated appropriately. If the diagnosis of deep vein thrombosis, pulmonary embolus, or non-cardiac, non-neurologic arterial thrombosis is confirmed, the subject must be discontinued from study drug.

Management of Select Laboratory Abnormalities

For any given laboratory abnormality, the investigator should assess the subject and apply the standard of care for medical evaluation and treatment following any local guidelines. Specific toxicity management guidelines for abnormal laboratory values are described in [Table 4](#) and may require a supplemental eCRF to be completed (see Section 6.1 Complaints and Adverse Events). All abnormal laboratory tests that are considered clinically significant by the investigator will be followed to a satisfactory resolution. If a repeat test is required per [Table 4](#), the repeat testing must occur as soon as possible.

Table 4. Specific Toxicity Management Guidelines for Abnormal Laboratory Values

Laboratory Parameters	Toxicity Management Guidelines
Hemoglobin	
 • If hemoglobin < 8 g/dL interrupt study drug dosing and confirm by repeat testing with a new sample. • If hemoglobin decreases ≥ 3.0 g/dL from baseline without an alternative etiology, interrupt study drug dosing and confirm by repeat testing with new sample. • If hemoglobin decreases ≥ 3.0 g/dL from baseline and an alternative etiology is known, the subject may remain on study drug at the investigator's discretion. 
If confirmed, continue to withhold study drug until hemoglobin value returns to normal reference range or its baseline value.

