
Aspartate transaminase (AST) or alanine transaminase (ALT)
	
 • Interrupt study drug immediately if confirmed ALT or AST > 3 × upper limit of normal (ULN) by repeat testing with new sample and either a total bilirubin > 2 × ULN or an international normalized ratio (INR) > 1.5. 
 • INR will only need to be measured in subjects with ALT or AST > 3 × ULN by the central lab. A repeat test of INR is not needed for determination if above toxicity management criteria are met. • Interrupt study drug immediately if confirmed ALT or AST > 3 × ULN by repeat testing with new sample along with appearance of fatigue, nausea, vomiting, right upper quadrant pain or tenderness, fever, rash, and/or eosinophilia (> 5%). • Interrupt study drug immediately if ALT or AST > 5 × ULN by repeat testing with new sample. • Interrupt study drug immediately if ALT or AST > 8 × ULN and contact the AbbVie TA MD. 
Subjects who meet any of the above criteria should be evaluated for an alternative etiology of the ALT or AST elevation and managed as medically appropriate. The investigator should contact the AbbVie Therapeutic Area MD (TA MD) to discuss the management of a subject when an alternative etiology has been determined. The alternative etiology should be documented appropriately in the eCRF; study drug should be discontinued if no alternative etiology can be found.
 
For any confirmed ALT or AST elevations > 3 ULN, complete supplemental hepatic eCRF.
 
 • Subjects with HBc Ab+ (irrespective of HBs Ab status) and negative HBV DNA at Screening who develop the following should have HBV DNA by PCR testing performed within one week: 
 • ALT > 5 × ULN OR • ALT or AST > 3 × ULN if an alternative cause is not readily identified. 
A positive result for HBV DNA PCR testing in these subjects will require immediate interruption of study drug (per local guidelines) and a hepatologist consultation should occur within one week for recommendation regarding subsequent treatment.

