8.2 Ethical Conduct of the Study

The study will be conducted in accordance with the protocol, Operations Manual, International Council for Harmonisation (ICH) guidelines, applicable regulations, and guidelines governing clinical study conduct and the ethical principles that have their origin in the Declaration of Helsinki. Responsibilities of the investigator are specified in [Appendix B](#).

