A negative result for HBs Ag will trigger automatic reflex testing for core antibodies (HBc Ab) and surface antibodies (HBs Ab).

- A negative test result for HBc Ab does not require HBV DNA PCR qualitative testing, and the subject may be enrolled ([Figure 1](#), Scenarios A and B).
- For a subject who has had an HBV vaccination (should document in the medical history), a positive test result for HBs Ab is expected. The HBV DNA PCR qualitative testing is not required, and the subject may be enrolled ([Figure 1](#), Scenario B).*
- A positive test result for HBc Ab requires HBV DNA PCR testing (automatic reflex testing) ([Figure 1](#), Scenarios C and D).
 - A result that exceeds detection sensitivity by central laboratory will be considered a positive result for HBV DNA and will be exclusionary.
 - A subject with a negative result for HBV DNA may be enrolled.
- Where mandated by local requirements: A positive result for HBs Ab requires HBV DNA PCR testing.
 - A result that exceeds detection sensitivity by central laboratory will be considered a positive result for HBV DNA and will be exclusionary.
 - A subject with a negative result for HBV DNA may be enrolled.

- For subjects with HBs Ab+ and/or HBc Ab+ and negative HBV DNA at Screening, HBV DNA PCR test should be performed every 12 weeks. HBV DNA PCR testing every 12 weeks is not necessary when the subject has a history of HBV vaccine and HBs Ab+ and HBc Ab–.
- At any time during the study for subjects with HBc Ab+ (irrespective of HBs Ab status) and negative HBV DNA at Screening, a positive result for HBV DNA PCR testing accompanied by the following will require immediate interruption of study drug (per local guidelines) and a hepatologist consultation should occur within one week for recommendation regarding subsequent treatment:
 - Alanine transaminase (ALT) > 5 × upper limit of normal (ULN) OR
 - ALT/Aspartate transaminase (AST) > 3 × ULN and either a total bilirubin > 2 × ULN or international normalized ratio (INR) > 1.5 OR
 - ALT/AST > 3 × ULN along with clinical signs of possible hepatitis.

Figure 1. Interpretation and Management of HBV Serologic Test Results

HBc Ab = hepatitis B core antibody; HBs Ab = hepatitis B surface antibody; HBs Ag = hepatitis B surface antigen; HBV = hepatitis B virus; PCR = polymerase chain reaction

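### Operations Manual 3.13 omits a Table 4 trigger for acting on a positive HBV DNA in HBc Ab+ subjects, and its 12-weekly HBV DNA test has no row in the activity schedule

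*Protocol*

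**What the plan says.** Two operative texts deal with possible HBV reactivation in the same subset: subjects who are HBc Ab+, whatever their HBs Ab status, with negative HBV DNA at Screening.

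- **Protocol 6.2, Table 4 (AST/ALT row).** HBV DNA is to be tested within one week if ALT exceeds 5 × ULN, or if ALT or AST exceeds 3 × ULN "if an alternative cause is not readily identified". Then: "A positive result for HBV DNA PCR testing in these subjects will require immediate interruption of study drug (per local guidelines"), with a hepatologist consultation within one week.
- **Operations Manual 3.13, Hepatitis B Virus.** At any time in the study, "a positive result for HBV DNA PCR testing accompanied by the following will require immediate interruption of study drug (per local guidelines"). The conditions are ALT > 5 × ULN; ALT/AST > 3 × ULN with total bilirubin > 2 × ULN or INR > 1.5; or ALT/AST > 3 × ULN "along with clinical signs of possible hepatitis". Here too, "a hepatologist consultation should occur within one week for recommendation regarding subsequent treatment".

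The same part of 3.13 requires HBV DNA PCR every 12 weeks in subjects who are HBs Ab+ and/or HBc Ab+ with negative HBV DNA at Screening. It exempts vaccinated subjects who are HBs Ab+ and HBc Ab−.

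Appendix D presents itself as showing the activities required at every encounter. Its only hepatitis row is ticked at Screening, and footnote g mentions HBV DNA only as a Screening exclusion test. The visit lists in Operations Manual 2.1 follow the same pattern.

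**The concern.** The two HBV rules share one trigger, ALT > 5 × ULN, and differ on what must accompany a rise above 3 × ULN. Table 4 asks whether another cause is readily apparent. Section 3.13 asks for raised bilirubin or INR, or for clinical signs. A positive HBV DNA with a moderate, symptom-free enzyme rise and no other explanation meets the first test and fails the second.

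At stake is whether a subject with apparent HBV reactivation stays on an immunosuppressive study drug, and whether a hepatologist is consulted within a week. The missing schedule row bears on the same risk. The 12-weekly PCR is how a positive HBV DNA could be found before enzymes rise, and a site that orders tests from the schedule could overlook it.

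**Working it through.** No figure in the plan needs reproducing, so the check sets the rules side by side.

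**Table 4's general rules.** Apart from the HBV rule, Table 4 interrupts drug for:

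- confirmed ALT or AST > 3 × ULN with bilirubin > 2 × ULN or INR > 1.5;
- confirmed ALT or AST > 3 × ULN with a listed symptom or eosinophilia;
- ALT or AST > 5 × ULN ("Interrupt study drug immediately if ALT or AST > 5 × ULN by repeat testing with new sample");
- ALT or AST > 8 × ULN.

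The further instruction to discontinue if no other etiology is found applies only to subjects who meet one of these four. None of the four requires a hepatologist.

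**Four illustrative cases.** All are HBc Ab+, with HBV DNA negative at Screening and now positive. The phrase *these subjects* in Table 4 is read as those who have had the listed enzyme event.

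| Case | Table 4 HBV rule | 3.13 HBV rule | Table 4 general rules |
|---|---|---|---|
| A. ALT 4 × ULN, AST normal, no other cause, bilirubin ≤ 2 × ULN, INR ≤ 1.5, no symptoms | Act: 4 > 3 and no cause found | Not met: 4 is not > 5; no bilirubin, INR or clinical-sign condition | Not met: 4 is not > 5; no accompanying condition |
| A′. As A, but ALT normal and AST 6 × ULN | Act: 6 > 3 and no cause found | Not met: its > 5 limb names ALT only | Interrupt on repeat test: 6 > 5; no consultation |
| B. ALT 4 × ULN, other cause identified, bilirubin 2.5 × ULN | Not met: cause identified and 4 is not > 5 | Act: 4 > 3 and 2.5 > 2 | Interrupt once confirmed; no consultation |
| C. ALT and AST normal | Not met | Not met | Not met |

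- **Case A** is the substantive gap. Table 4's HBV rule is the only text that stops drug.
- **Case A′** differs only in the consultation, because the general AST rule interrupts.
- **Case B** also differs only in the consultation, which 3.13 alone requires. The version of B with clinical signs in place of raised bilirubin behaves the same way if 3.13's clinical signs correspond to Table 4's symptom list. Table 4's list is explicit and includes fatigue, fever and rash; 3.13 gives no list.
- **Case C** is what routine 12-weekly testing could find. On this reading neither text gives an action.

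**The wider reading.** If *these subjects* means every HBc Ab+ subject with negative HBV DNA at Screening, Table 4 acts on any positive result. It then contains 3.13 entirely: B is no longer a discrepancy, A and A′ remain, and C becomes a case where only Table 4 acts.

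**Schedule.** Counting from Baseline, which is my inference, every 12 weeks gives Weeks 12, 24 and 36 on treatment and Week 48 at its end: 3 to 4 tests per subject in the subset. All four are existing visits. Being conditional does not explain the missing row, because urine pregnancy tests (women of childbearing potential), skin photographs (lupus rash) and BTK occupancy (selected US sites) all have rows.

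**The case against.** The strongest reply is that the rules do not contradict each other. Each states conditions sufficient for action, and neither says to act only then or to continue dosing otherwise. Protocol 8.2 binds sites to both ("The study will be conducted in accordance with the protocol, Operations Manual"), and Section 6.2 sends readers to Table 4 for laboratory toxicity ("Specific toxicity management guidelines for abnormal laboratory values are described in"). Both HBV rules defer to local guidelines, and Section 5.5 lets the investigator stop drug for clinically significant laboratory results or in the subject's interest. This stands. A reader might infer that a site cannot comply with both texts, but it can, and in case A doing so means interrupting. What remains is that neither HBV rule refers to the other and 3.13 reads as complete, so a site using it alone has no instruction to stop.

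It may also be said that Table 4 governs for-cause testing and 3.13 routine testing. That does not resolve case A, because 3.13 applies at any time during the study.

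On the schedule, Appendix D refers to the Operations Manual for detail, HBV DNA is in the laboratory table, and another subset test, the Japan-only beta-D-glucan, also lacks a row. A reader might infer that on-study HBV DNA monitoring is not required. It is required, in 3.13, so this is a scheduling gap and no more.

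**Conclusion.** The point holds within limits. For HBc Ab+ subjects with negative HBV DNA at Screening, 3.13 lacks Table 4's trigger of ALT or AST > 3 × ULN with no readily identified alternative cause. With neither enzyme above 5 × ULN, bilirubin and INR within limits and no symptoms, no general Table 4 rule fills the gap. Case B is a lesser mismatch about the consultation alone. The 12-weekly test is missing from the schedule and visit lists.

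A reader might infer that the wider reading of *these subjects* makes the mismatch larger throughout. The texts do not support that: it enlarges the set of subjects whom only Table 4 would interrupt, and it removes case B.

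Few subjects are likely to be affected; the documents give no number, and none can be derived from them. Figure 1 of the Operations Manual, on managing HBV serology results, is not reproduced in the text and could not be checked. The point has no bearing on sample size, significance level or the efficacy analysis.

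**What to change.** 1. Give both HBV rules the same triggers and cross-refer them. Add to 3.13 the trigger of ALT or AST > 3 × ULN with no readily identified alternative cause. Add to Table 4's HBV rule the bilirubin/INR and clinical-signs triggers from 3.13.
2. State whether *these subjects* in Table 4 means all HBc Ab+ subjects with negative HBV DNA at Screening. If it does, any positive HBV DNA triggers action and 3.13 should be aligned to that, so that harmonising does not weaken Table 4.
3. Add an HBV DNA PCR row at Weeks 12, 24, 36 and 48 to Appendix D and the visit lists, footnoted to the subset and exemption in 3.13.

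The cost is one amendment to Table 4, Appendix D and the Operations Manual. It adds no visits and no scheduled tests beyond those 3.13 already requires. The downside is possibly a few extra interruptions or consultations. Under Operations Manual 6.1, missing more than 10 days of drug in the first 24 weeks, or more than 30 days afterwards, is a protocol deviation.

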
Serum Creatinine
	
 • If serum creatinine is > 1.5 × the baseline value and > ULN, repeat the test for serum creatinine (with subject in an euvoletic state) to confirm the results. If the results of the repeat testing still meet this criterion then interrupt study drug and re-start study drug once serum creatinine returns to ≤ 1.5 × baseline value and ≤ ULN. • If confirmed new serum creatinine ≥ 2 mg/dL interrupt study drug, and re-start study drug once serum creatinine returns to normal reference range or its baseline value. 
For the above serum creatinine elevation scenarios, complete supplemental renal eCRF(s).

Laboratory Parameters	Toxicity Management Guidelines
Creatine Phosphokinase (CPK)	
 CPK and aldolase will be measured at every visit but results will be blinded to sites and subjects, as CPK elevation is a known class effect of JAK inhibitors and the results could be unblinding to the sites. If symptomatic myositis is suspected, the site may send a request to the AbbVie TA MD for CPK and/or aldolase results to be unblinded. Request must be approved by the AbbVie TA MD. If confirmed CPK $\geq 4 \times$ ULN accompanied by symptoms suggestive of myositis or rhabdomyolysis, interrupt study drug, complete supplemental CPK eCRF, and contact AbbVie TA MD.
Lymphocyte Count Decreased	
 If confirmed Grade 4 ($< 200/\text{mm}^3$) by repeat testing with new sample, interrupt study drug dosing until lymphocyte count returns to at least Grade 2 (< 800 to $500/\text{mm}^3$) or its baseline value.
White Blood Cell Count Decreased	
 If confirmed Grade 4 ($< 1000/\text{mm}^3$) by repeat testing with new sample, interrupt study drug dosing until white blood cell count returns to at least Grade 2 (< 3000 to $2000/\text{mm}^3$) or its baseline value.
Urine Protein to Creatinine Ratio	
 If > 1 g/day equivalent (1 mg/mg), repeat by testing with new sample, and if confirmed, a renal biopsy will be required. If Class IV lupus nephritis is confirmed, subject must be permanently discontinued from study drug.

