3.13 Clinical Laboratory Tests

The blood samples for serum chemistry tests should be collected following a minimum 8-hour fast prior to study drug intake (with the exception of the Screening visit, which may be nonfasting). Subjects whose visits occur prior to the morning dose of study drug should be instructed to fast after midnight until the blood sample is collected in the morning and thereafter take their study drug with food. Subjects whose visits occur after the morning dose of study drug should be instructed to fast after breakfast until the study visit occurs. At the Study Day 1 visit, a fasting blood sample should be collected prior to the first dose of study drug. Blood samples should still be drawn if the subject did not fast for at least 8 hours. Fasting or nonfasting status will be recorded in the source documents and on the laboratory requisition. The baseline laboratory test results for clinical assessment for a particular test will be defined as the last measurement prior to the initial dose of study drug.

A certified laboratory will be utilized to process and provide results for the clinical laboratory tests. Laboratory reference ranges will be obtained prior to the initiation of the study.

Instructions regarding the collection, processing, and shipping of these samples will be provided by the central laboratory.

If a laboratory test value is outside the reference range and the investigator considers the laboratory result to be clinically significant, the investigator will:

- repeat the test to verify the out-of-range value;
- follow the out-of-range value to a satisfactory clinical resolution; or
- discontinue the subject from study drug or require the subject to receive treatment; in this case, the laboratory result will be recorded as an AE.

If renal and hematological laboratory results required for physician indices are not available (e.g., specimen hemolyzed, specimen lost in transit, specimen received beyond stability, etc.), re-draw should occur within 7 days of notification from Labcorp Drug Development that results are unavailable.

Clinical Laboratory Tests ^a		
HEMATOLOGY	CLINICAL CHEMISTRY	URINALYSIS

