Hematocrit Hemoglobin Red Blood Cell (RBC) count/ Erythrocytes White Blood Cell (WBC) count/ Leukocytes Platelet count/Thrombocytes Prothrombin Partial thromboplastin Differential Automatic (absolute count): Neutrophils Eosinophils Basophils Monocytes Lymphocytes Manual Differential (ONLY IF Automated Differential is abnormal): Neutrophils, bands (stabs) Neutrophils, polymorphonuclear (PMN) Eosinophils Basophils Monocytes Lymphocytes	Electrolytes Calcium Sodium Potassium Chloride Bicarbonate Substrates Glucose Blood urea nitrogen Creatinine (Glomerular Filtration Rate [GFR]) Bilirubin Total Bilirubin Direct (if total is elevated) Bilirubin Indirect (if total is elevated) Albumin Cholesterol, total Low-density lipoprotein cholesterol High-density lipoprotein cholesterol Triglycerides Follicle-stimulating hormone (FSH) ^b Cotinine Enzymes Aspartate transaminase (AST/GOT) Alanine transaminase (ALT/GPT) Alkaline phosphatase Creatine phosphokinase (CPK) ^c Aldolase ^c	Dipstick Urinalysis Urine Nitrite Urine Protein Urine Glucose Urine Ketone Urobilinogen Urine Bilirubin Urine RBC/Erythrocytes Urine WBC/Leukocytes Urine pH Urine creatinine Urine-Sediment (microscopic examination, only if urine analysis abnormal) Urine Sediment Bacteria Urine Cast in Sediment Urine Squamous Epithelial Cells Urine Sediment Crystals, Unspecified Urine Sediment RBC/Erythrocytes Urine Sediment WBC/Leukocytes Urine Urine Protein to Creatinine Ratio

INFECTIOUS SCREENING	PREGNANCY TESTING	PHARMACOKINETIC/ PHARMACODYNAMIC
HBs Ag (qualitative) HBs Ab (qualitative) Anti-HBc total (qualitative) HBV DNA (quantitative) HCV Ab (qualitative) HCV RNA (quantitative) HIV-1 and HIV-2 Ab (qualitative) QuantiFERON®-TB and/or PPD Beta-D-glucan (for Japan subjects only)	Urine pregnancy test (local) Serum pregnancy test	Plasma elsubrutinib and upadacitinib concentration
	CENTRAL LAB^a	SPECIALTY LAB
	B cell subsets and TBNK cells ANA Anti-Smith Anti-dsDNA Complement C3, C4 IgG and IgM Anticardiolipin antibody Anti-beta 2 glycoprotein 1 antibody Lupus anticoagulant	Blood sample for BTK occupancy analyses (only select number of sites and subjects in the US) Blood sample for BTK Y223 IFN signature

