Ab = antibody; ANA = antinuclear antibody test; COVID-19 = coronavirus disease 2019; BTK = Bruton's tyrosine kinase; dsDNA = double-stranded deoxyribonucleic acid; GOT = glutamic oxaloacetic transaminase; GPT = glutamic pyruvic transaminase; HBV = hepatitis B virus; HBC = Hepatitis B core (antibody); HBs Ab = hepatitis B surface antibody; HBs Ag = hepatitis B surface antigen; HCV = hepatitis C virus; HIV = human immunodeficiency virus; IFN = interferon; IgG = immunoglobulin G; IgM = immunoglobulin M; JAK = Janus kinase; PPD = purified protein derivative; TA MD = Therapeutic Area Medical Director; TB = tuberculosis; TBNK = T lymphocytes, B lymphocytes, and natural killer lymphocytes; US = United States

- Tests may also be performed by a certified local lab if sending samples to the central lab is not possible due to COVID-19-related restrictions.
- Performed only at Screening.
- CPK and aldolase will be measured at every visit but results will be blinded to sites and subjects, as CPK elevation is a known class effect of JAK inhibitors and the results could be unblinding to the sites. If symptomatic myositis is suspected, the site may send a request to the AbbVie TA MD for CPK and/or aldolase results to be unblinded. Request must be approved by the AbbVie TA MD.

Pregnancy Testing (Serum and Urine)

Pregnancy testing should not be performed for women who are not of childbearing potential, as described above.

A quantitative serum pregnancy test will be performed at Screening and a urine pregnancy test will be performed at Baseline.

The serum pregnancy test will be sent to and performed by the central laboratory. If the serum pregnancy test is positive the subject is considered a screen failure. If the serum pregnancy test is borderline, it should be repeated ≥ 3 days later to determine eligibility.

If the repeat serum pregnancy test is:

- Positive, the subject is considered a screen failure;
- Negative, the subject can be enrolled into the trial;

- Still borderline, ≥ 3 days later, this will be considered documentation of continued lack of a positive result and the subject can be enrolled into the study (unless prohibited per local requirements) in the absence of clinical suspicion of pregnancy and other pathological causes of borderline results.

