* A positive test result for HBs Ab is expected for subjects who have had an HBV vaccination. For subjects without a history of HBV vaccination (and for subjects in Japan and China or where mandated by local requirements), a positive result for HBs Ab/anti-HBs requires HBV DNA PCR testing.

Hepatitis C Virus

Blood samples for HCV serology will be obtained at the Screening visit. A positive HCV Ab will trigger an HCV RNA test. A subject will not be eligible for study participation if test results indicate active hepatitis C (HCV RNA detectable in any subject with anti HCV Ab).

HIV

Subjects with HIV infection (positive HIV test) are excluded from study participation. HIV testing will be performed at Screening, unless prohibited by local regulations. The investigator must discuss any local reporting requirements to local health agencies with the subject. The site will report confirmed positive results to their health agency per local regulations, if necessary. If a subject has a confirmed positive result, the investigator must discuss with the subject the potential implications to the subject's health, and subject should receive or be referred for clinical care promptly.

COVID-19 Pandemic-Related Acceptable Protocol Modifications

If travel restrictions or other changes in local regulations, or changes in shipping logistics in light of the coronavirus disease 2019 (COVID-19) pandemic prevent the subject from having blood drawn and analyzed for laboratory testing at the study site, if possible, arrange for subjects to have laboratory work done at a local lab, hospital, or other facility. Local lab results should be obtained along with reference ranges and kept within the subjects' source documentation. Local lab results should be reviewed by the investigator as soon as possible.

If laboratory samples cannot be obtained, study drug administration may be continued for 1 month provided the investigator has reviewed all prior laboratory results and confirms and discusses with the subject that there is no safety concern for the subject to continue use of the study drug in the absence of current labs. The subject should be scheduled for laboratory draws as soon as feasible.

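### The COVID-19 local-laboratory provision conflicts with the rule masking CPK and aldolase from sites, and no route is given for keeping a local result masked

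*Protocol*

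**What the plan says.** **Masking rule.** Operations Manual 3.13, footnote c, states: "CPK and aldolase will be measured at every visit but results will be blinded to sites and subjects". Protocol 6.2, Table 4, has the same rule and gives the reason: "as CPK elevation is a known class effect of JAK inhibitors and the results could be unblinding to the sites". One release route is described. If symptomatic myositis is suspected, the site may ask the sponsor's medical director for the values, and "Request must be approved by the AbbVie TA MD".

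**Local-laboratory provision.** In Operations Manual 3.13, CPK and aldolase are listed among the chemistry enzymes in a table headed "Clinical Laboratory Tests ^a". Footnote a to that heading reads: "Tests may also be performed by a certified local lab if sending samples to the central lab is not possible due to COVID-19-related restrictions". The COVID-19 modifications at the end of 3.13 apply when travel limits, local rules or shipping problems prevent testing through the study site. Results are then obtained from a local laboratory, hospital or other facility and filed with the subject's source documents. The text adds: "Local lab results should be reviewed by the investigator as soon as possible".

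**Blinding standard.** Protocol 5.8 keeps the investigator, site staff and subject blinded for the whole study. Sponsor staff who directly oversee the trial are blinded until the Week 24 primary efficacy analysis is complete.

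**The concern.** The sponsor judged CPK informative enough about treatment to withhold it from sites. That works when the central laboratory controls what is reported. A local laboratory or hospital normally reports to whoever ordered the test, and here that report goes to the investigator for review.

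The activity schedule lists PhGA, SLEDAI-2K and BILAG as investigator assessments, and these are the three components of SRI-4. PhGA is a physician's rating on a visual analogue scale. The primary endpoint also requires a steroid dose of at most 10 mg, and steroid tapering is the one permitted change to background therapy (Protocol 5.4). The person told to read the local report therefore produces or oversees most of the primary-endpoint data. A hint about treatment could influence those ratings and decisions.

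**Working it through.** The plan gives no figure to reproduce. The main check is a comparison of the texts, followed by a bound under stated assumptions.

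**Text comparison**

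1. *Are the two tests due at the affected visits?* Yes. Footnote c and Table 4 both say every visit.
2. *Does the local-laboratory permission cover them?* Yes, on its wording. Footnote a is attached to the heading of the whole table and excepts no test. It is attached again to the central-laboratory sub-heading, but the enzymes come in through the main heading. The COVID-19 modifications speak of laboratory testing in general.
3. *Where do local results go?* To site source documents and the investigator, with no test excepted.
4. *Is there a masking route for a local report?* None is stated. Nothing suppresses the two lines or directs them to another reader.
5. *Does footnote c lapse under COVID-19?* No. It has no such exception.

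Steps 3 and 5 cannot both be met for a local report that contains CPK or aldolase unless a route is supplied, and step 4 finds none.

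**How informative one value could be**

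Groups 1, 2 and 4 contain upadacitinib. With equal allocation the prior chance of upadacitinib is 3/5 = 60%, and of double placebo 1/5 = 20%. The documents give no CPK elevation rates, so two scenarios are assumed:

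| | 20% on upadacitinib, 5% otherwise | 10% on upadacitinib, 5% otherwise |
|---|---|---|
| Chance of a raised value | 0.6×0.20 + 0.4×0.05 = 0.14 | 0.6×0.10 + 0.4×0.05 = 0.08 |
| Upadacitinib, given raised | 0.12/0.14 = 86% | 0.06/0.08 = 75% |
| Double placebo, given raised | 0.2×0.05/0.14 = 7% | 0.2×0.05/0.08 = 12.5% |
| Upadacitinib, given normal | 0.48/0.86 = 56% | 0.54/0.92 = 59% |

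A raised value is informative. A normal one barely moves the 60% prior.

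**How many subjects**

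The documents do not say how many subjects used a local laboratory. Assume 2% to 10% of 325, which is 6.5 to 32.5 subjects. Multiply by the chance of a raised value, taken once per subject:

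- Low end: 6.5 × 0.08 = 0.52
- High end: 32.5 × 0.14 = 4.55

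That is about 0.5 to 5 subjects with a raised local CPK. Repeated local visits by the same subject would increase the number.

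**The case against.** A reader might infer that the COVID-19 provision sends the full chemistry panel, CPK included, to the investigator, so that a site following the manual sees CPK at every local-laboratory visit. The documents do not support that. The provision names neither CPK nor a full panel, footnote a is permissive, and footnote c still requires masking. This is a conflict between instructions, not an instruction to unmask. The Operations Manual also refers to a study-specific laboratory manual and to central-laboratory instructions. These are not in the documents and may contain a working arrangement.

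Other points reduce the likely effect:

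- When travel limits keep a subject away, the efficacy assessments may be missing too, and SAP 8.3 provides multiple imputation for COVID-19 missingness. This stands in part. Shipping failure is also a trigger, and then the subject may still be assessed at the site. Knowledge from one visit can also carry over to later ratings.
- Operations Manual 3.11 asks for an independent, blinded joint assessor where possible. That protects the joint counts but not PhGA or the rest of SLEDAI-2K and BILAG.
- Protocol 2.2 lists neutropenia and hypercholesterolemia as possibly related to upadacitinib. Neutrophils and cholesterol are in the panel without a masking footnote, so sites may already have some treatment-related signal. This stands, and it makes the added information from CPK smaller.
- Uneven exposure across regions is plausible but undocumented. Randomization should balance local-laboratory use between arms in expectation.

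**Conclusion.** The conflict is real and can be shown from the text alone. Two sections require masking; a footnote and a COVID-19 provision allow local testing with investigator review; nothing says how to satisfy both. The point is worth correcting because the safeguard is one the sponsor says it needs and the exposed reader rates the primary-endpoint components.

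The problem is small. It is limited to COVID-affected visits at which a local laboratory ran CPK or aldolase; central-laboratory visits stay masked. Neither the number of such visits nor the size of any bias can be derived from the documents. The figure of about 0.5 to 5 subjects with a raised local CPK rests wholly on assumed rates of local-laboratory use (2% to 10%) and CPK elevation (20% or 10% on upadacitinib, 5% otherwise). It shows scale only. The documents do not support a conclusion that the blind was broken or that the primary comparison is materially biased.

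**What to change.** Reconcile Protocol Table 4, footnotes a and c of Operations Manual 3.13, and its COVID-19 modifications. One sentence in 3.13 would do it: any CPK or aldolase result from a local laboratory is reported to a named recipient outside both the blinded site and the blinded study team, and is withheld from the site. The recipient has to be specified because, under Protocol 5.8, sponsor staff with direct oversight are themselves blinded through Week 24. Every-visit measurement and the existing request route through the sponsor's medical director stay as written. Leaving the two tests off local panels would contradict the every-visit rule, to which a Table 4 drug-interruption criterion is linked, so it is not proposed here.

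Also record in the eCRF each visit at which a site saw a local CPK or aldolase value, and list those subjects by arm. This is useful for past visits too, and it would replace the assumed exposure with a count.

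The cost is one sentence, a note to sites and one eCRF item. The downside is extra handling, and these values may become available later at COVID-affected visits.
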